3.4 SELECTION OF STUDY POPULATION

3.4.1 Inclusion Criteria

Eligible subjects will be considered for inclusion in this study if they meet **all** of the following criteria:

1. Men and women ≥ 18 years of age.
2. Eastern Cooperative Oncology Group (ECOG) performance status of ≤ 2 .
3. Pathologically confirmed de novo ABC DLBCL, and subjects **must have** available archival tissue for central pathology review to be eligible.
4. Relapsed or refractory disease, defined as either: 1) recurrence of disease after a CR, or 2) PR, SD, or progressive disease at completion of the treatment regimen preceding entry to the study (residual disease):
 - Subjects must have previously received a standard anthracycline and rituximab-based first-treatment regimen (eg, R-CHOP).
 - Subjects with suspected residual disease after the treatment regimen directly preceding study enrollment must have biopsy demonstration of residual DLBCL.
 - Subjects who have not received HDT/ASCT must be ineligible for HDT/ASCT as defined by meeting any of the following criteria:
 - Age ≥ 70 years
 - Diffuse lung capacity for carbon monoxide (DLCO) $< 50\%$ by PFT
 - Left ventricular ejection fraction (LVEF) $< 50\%$ by ECHO
 - Other organ dysfunction or comorbidities precluding the use of HDT/ASCT on the basis of unacceptable risk of treatment-related morbidity
 - Subject refusal of HDT/ASCT
 - Subjects who are intolerant to anthracycline-based first-line therapy and meet all other eligibility criteria including recurrent or refractory disease are also eligible.
5. Presence of radiographically measurable lymphadenopathy or extranodal lymphoid malignancy (defined as the presence of ≥ 1 lesion that measures ≥ 2.0 cm in the longest dimension and ≥ 1.0 cm in the longest perpendicular dimension as assessed by CT scan).
6. Agreement to use acceptable forms of contraception during the study and for 30 days after the last dose of study drug if sexually active and able to bear or beget children.

7. Agreement to refrain from sperm donation during the study and for 30 days after the last dose of study drug.
8. Willing and able to participate in all required evaluations and procedures in this study protocol including swallowing capsules without difficulty.
9. Ability to understand the purpose and risks of the study and provide signed and dated informed consent and authorization to use protected health information (in accordance with national and local patient privacy regulations).

3.4.2 Exclusion Criteria

Subjects will be ineligible for this study if they meet **any** of the following criteria:

1. Transformed DLBCL or DLBCL with coexistent histologies (eg, FL or MALT)
2. Primary mediastinal (thymic) large B-cell lymphoma (PMBL)
3. Known central nervous system (CNS) lymphoma
4. Prior malignancy, except for adequately treated basal cell or squamous cell skin cancer, in situ cervical cancer, or other cancer from which the subject has been disease free for ≥ 2 years or which will not limit survival to < 2 years. Note: these cases must be discussed with the medical monitor.
5. A life-threatening illness, medical condition, or organ system dysfunction which, in the investigator's opinion, could compromise the subject's safety, interfere with the absorption or metabolism of *acalabrutinib*, or put the study outcomes at undue risk.
6. Significant cardiovascular disease such as uncontrolled or symptomatic arrhythmias, congestive heart failure, or myocardial infarction within 6 months of screening, or any Class 3 or 4 cardiac disease as defined by the New York Heart Association Functional Classification, or QTc > 480 msec.
7. Malabsorption syndrome, disease significantly affecting gastrointestinal function, or resection of the stomach or small bowel, gastric bypass, symptomatic inflammatory bowel disease, or partial or complete bowel obstruction.
8. Any immunotherapy within 4 weeks of first dose of study drug.
9. The time from the last dose of the most recent chemotherapy or experimental therapy to the first dose of study drug is < 5 times the half-life of the previously administered agent(s).
10. Radio- or toxin-immunoconjugates within 10 weeks of the first dose of study drug
11. Prior exposure to a B-cell receptor (BCR) inhibitor (eg, Btk phosphoinositide-3 kinase [PI3K], or Syk inhibitors) or BCL-2 inhibitors (eg, ABT-199).
12. Grade ≥ 2 toxicity (other than alopecia) continuing from prior anticancer therapy including radiation.
13. Known history of human immunodeficiency virus (HIV), serologic status reflecting active hepatitis B or C infection, or any uncontrolled active systemic infection. Subjects with hepatitis B core antibody positive who are surface antigen negative or who are hepatitis C antibody positive will need to have a negative PCR result before enrollment. Those who are hepatitis B surface antigen positive or hepatitis B PCR positive and those who are hepatitis C PCR positive will be excluded.
14. Major surgery within 4 weeks before first dose of study drug.

15. History of stroke or intracranial hemorrhage within 6 months before the first dose of *acalabrutinib*.
16. History of bleeding diathesis (eg, hemophilia or von Willebrand disease)
17. Requires or receiving anticoagulation with warfarin or equivalent vitamin K antagonists (eg, phenprocoumon) within 28 days of first dose of study drug.
18. Requires treatment with long-acting proton pump inhibitors (eg, omeprazole, esomeprazole, lansoprazole, dexlansoprazole, rabeprazole, or pantoprazole)
19. Any of the following laboratory abnormalities:
 - a. Absolute neutrophil count (ANC) < 750 cells/mm³ (0.75×10^9 /L). For subjects with documented bone marrow involvement, ANC < 500 cells/mm³ (0.50×10^9 /L)
 - b. Platelet count $< 50,000$ cells/mm³ (50×10^9 /L) independent of transfusion support. For subjects with documented bone marrow involvement, $< 30,000$ cells/mm³ (30×10^9 /L)
 - c. Serum AST/SGOT or ALT/SGPT $\geq 3.0 \times$ ULN
 - d. Creatinine $> 2.5 \times$ ULN
 - e. Total bilirubin $> 2.5 \times$ ULN
20. Breast feeding or pregnant.
21. Concurrent participation in another therapeutic clinical trial.

3.4.3 Replacement of Subjects

Any subject who does not complete Cycle 2 may be replaced at the discretion of the study investigator and sponsor.

3.4.4 Enrollment Procedures

Enrollment of a subject into the study will be performed according to the following procedure:

- The study center will notify the sponsor when a clinically eligible subject is identified and is ready to screen, to ensure enrollment availability on the study.
- After the subject has signed and dated the Informed Consent Form (ICF), all screening procedures have been completed, and eligibility has been confirmed, the subject can be officially enrolled in the study.
- To enroll a subject, the study center will fax/email a completed Enrollment Confirmation Form to the sponsor. The enrollment date will be the date that the form is faxed/emailed to the sponsor.
- An Enrollment Confirmation Form will be completed and faxed/emailed to the study center by the sponsor within 24 hours.

Treatment must begin within the screening window ([Section 4.1](#)) and after the site has received notification from the sponsor. Study treatment is not blinded on this study.

3.5 STUDY DRUG

3.5.1 Premedications

No specific premedications or supporting medications are required in conjunction with *acalabrutinib* administration.

3.5.2 Formulation, Packaging, and Storage

Acalabrutinib should be stored according to the instructions on the label that is affixed to the package containing the drug product.

Acalabrutinib capsules contain 100 mg drug substance. *Acalabrutinib* will be provided in white, high-density polyethylene bottles.

If a drug shipment arrives damaged, or if there are any other drug complaints, a SAE/Product Complaint Form should be completed and emailed or faxed to the sponsor or the sponsor's representative.

Refer to the Investigator Brochure for additional information.

3.5.3 Administration of Study Drug

Investigators are prohibited from supplying *acalabrutinib* to any subjects not properly enrolled in this study or to any physicians or scientists except those designated as subinvestigators on FDA Form 1572. The investigator must ensure that subjects receive *acalabrutinib* only from personnel who fully understand the procedures for administering the drug.

Acalabrutinib is intended to be administered orally with 8 ounces (approximately 240 mL) of water. Subjects may take study drug with or without food. The capsules should be swallowed intact and subjects should not attempt to open capsules or dissolve them in water. Dietary restrictions are provided in [Section 3.7.1](#).

Doses should be taken BID with the second dose 11-13 hours after the first.

If a dose is missed, it can be taken within 3 hours after the scheduled time with a return to the normal schedule with the following dose. If the time from the scheduled time of administration has been > 3 hours, the dose should not be taken, and the subject should take the next dose at the scheduled time. The missed dose will not be made up and must be returned to the site at the next scheduled visit.

3.5.4 Assuring Subject Compliance

Subjects will receive their Day 1 and Day 8 doses in the clinic. For treatments that are taken in the clinic, subjects should take the dose from the drug dispensed for them for that particular time period. All other treatments will be taken at home. Subjects will receive a diary to record the specific time each dose was taken and to record reasons for any missed doses.

Subject compliance will be assessed at every visit. The subject will be instructed to bring the diary and any remaining capsules to the clinic at their next visit. The administrator will review the diary and ask the subject if all of the capsules were administered. Any remaining or returned capsules will be counted and recorded as described in [Section 7.7](#). Returned capsules must not be redispensed to another subject. The study staff will resupply the subject with the correct number of capsules needed for use until the next visit.

3.5.5 Dose Delays

Treatment with *acalabrutinib* should be held for any unmanageable, potentially study drug-related toxicity that is Grade ≥ 3 in severity. Any other clinically important events where dose delays may be considered appropriate by the investigator must be discussed with the medical monitor. Study drug may be held for a maximum of 28 consecutive days from expected dose due to toxicity. Study treatment should be discontinued in the event of a toxicity lasting > 28 days, unless reviewed and approved by the medical monitor.

Note: temporary withholding of study drug for as little as 7 days can cause a transient worsening of disease and/or of constitutional symptoms. Refer to [Section 3.8](#) for more information on assessing disease progression under these circumstances.

3.5.6 Dose Modification and Discontinuation

The actions in [Table 3-1](#) should be taken for the following toxicities:

- Grade 4 ANC (< 500/ μ L) for > 7 days (Neutrophil growth factors are permitted per ASCO guidelines [[Smith 2006](#)] and use must be recorded on the electronic case report form [eCRF]).
- Grade 3 platelets in presence of significant bleeding
- Grade 4 platelets

- Grade 3 or 4 nausea, vomiting, or diarrhea, if persistent despite optimal antiemetic and/or anti-diarrheal therapy
- Any other Grade 4 toxicity or unmanageable Grade 3 toxicity.

Table 3-1. Drug Discontinuation Actions for *Acalabrutinib*

| Occurrence | Action |
|------------|--|
| 1st - 2nd | Hold acalabrutinib until recovery to Grade \leq 1 or baseline; may restart at original dose level |
| 3rd | Hold acalabrutinib until recovery to Grade \leq 1 or baseline; restart at 100 mg once daily |
| 4th | Discontinue acalabrutinib |

Whenever possible, any dose adjustment of *acalabrutinib* should be discussed between the investigator and the Acerta Pharma medical monitor before implementation. The appropriate clinic staff should dispense the study drug for the new dose level and instruct the subject/caregiver about the change in dose level. Any changes to the dosing regimen must be recorded in the Dosage Administration eCRF.

3.6 CONCOMITANT THERAPY

3.6.1 Permitted Concomitant Therapy

Antiemetics are permitted if clinically indicated. Standard supportive care medications are permitted as per institutional standards.

For subjects considered at risk for tumor lysis syndrome: Administer appropriate hydration, alkalinization of urine, and allopurinol or rasburicase per institutional standards before initiating treatment.

3.6.2 Guideline for Use of CYP Inhibiting/Inducing Drugs

At the systemic exposure levels expected in this study, *acalabrutinib* inhibition of CYP metabolism is not anticipated. However, concomitant administration of *acalabrutinib* with a strong CYP3A4 inhibitor increased exposure by approximately 5-fold (see *Investigator Brochure*). Consequently, the concomitant use of strong inhibitors/inducers of CYP3A4 ([Appendix 2](#)) should be avoided when possible. *Subjects requiring long-term (>1 week) treatment with a strong CYP3A inhibitor/inducer are excluded from the study. In addition, the use of strong or moderate CYP3A inhibitors or inducers within 7 days of the first dose of study drug is prohibited. If a subject requires short-term treatment (\leq 7 days) with a strong*

CYP3A inhibitor, acalabrutinib treatment should be interrupted. If the subject requires treatment with a moderate CYP3A inhibitor, the acalabrutinib dose should be reduced to 100 mg QD. Co-administration of strong CYP3A inducers should be avoided. If a subject requires treatment with a strong CYP3A inducer, the acalabrutinib dose should be increased to 200 mg BID.

3.6.3 Guideline for Use of Drugs that Affect Gastric pH

Use of proton-pump inhibitors, H₂-receptor antagonists, or antacids while taking acalabrutinib is not recommended due to a potential decrease in study treatment exposure. If treatment with a gastric acid reducing agent is required, use of a H₂-receptor antagonist (2 hours after acalabrutinib) or antacid (2 hours before or 2 hours after acalabrutinib) should be considered. Co-administration of acalabrutinib with proton pump inhibitors should be avoided.

The concomitant use of acalabrutinib with BCRP substrates (e.g., prazosin, glyburide, nitrofurantoin, dipyridamole, statins, and cimetidine) may increase exposure to the BCRP substrates by inhibition of intestinal BCRP, and therefore should be avoided.

3.6.4 Prohibited Concomitant Therapy

Any chemotherapy, immunotherapy, corticosteroids (> 10 mg of prednisone or equivalent), kinase inhibitors, bone marrow transplantation, experimental therapy, warfarin, and radiotherapy are prohibited.

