3.7.3 Hemorrhage

Serious hemorrhagic events, including fatal events, have occurred in clinical trials with acalabrutinib.

The mechanism for hemorrhage is not well understood. Subjects receiving antithrombotic agents may be at increased risk of hemorrhage. Use caution with antithrombotic agents and consider additional monitoring for signs of bleeding when concomitant use is medically necessary. Consider the benefit-risk of withholding acalabrutinib for at least 3 days pre- and post-surgery. Subjects with hemorrhage should be managed per institutional guidelines with supportive care and diagnostic evaluations as clinically indicated.

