3.8 STOPPING RULES

All study participants may receive *acalabrutinib* indefinitely as long as they are safely benefitting. However:

- Any subject has the right to withdraw from the study at any time.
- Any subject who has objective evidence of definitive DLBCL progression while receiving study treatment at the highest individual tolerable dose level allowed in the protocol (see [Section 3.5.5](#)) should be withdrawn from the study treatment. Note: If there is uncertainty regarding whether there is DLBCL progression, the subject should continue study treatment and remain under close observation (eg, evaluated at 4- to 8-week intervals) pending confirmation of progression. In particular, transient worsening of disease during temporary interruption of study therapy (eg, for intercurrent illness, drug-related toxicity, or surgery) may not indicate disease progression. In such circumstances, and if medically appropriate, subjects may resume therapy and relevant clinical, laboratory, and/or radiographic assessment should be done to document whether tumor control can be maintained or whether actual disease progression has occurred.
- Any subject who is unable to tolerate rechallenge with the lowest protocol-described, dose-modified levels (see [Section 3.5.5](#)) should be withdrawn from the study treatment unless continued therapy is permitted by the Acerta Pharma medical monitor.
- Any subject whose medical condition substantially changes after entering the study should be carefully evaluated by the investigator in consultation with the Acerta Pharma medical monitor. Such subjects should be withdrawn from study treatment if continuing would place them at risk.
- Any subject who becomes pregnant or begins breastfeeding should be removed from study treatment.
- Any subject who becomes significantly noncompliant with study drug administration, study procedures, or study requirements should be withdrawn from study treatment in

circumstances that increase risk or substantially compromise the interpretation of study results.

- The investigator, in consultation with the Acerta Pharma medical monitor, may withdraw any subject from the study treatment, if, in the investigator's opinion, it is not in the subject's best interest to continue.

Subjects who discontinue study therapy will continue on study for safety ([Section 4.3](#)) and time-to-next therapy ([Section 4.4](#)) unless they withdraw consent for further follow-up.

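### Section 3.6.4 bans only warfarin on study, although criterion 17 groups it with equivalent vitamin K antagonists: a minor inconsistency with patient-safety relevance

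*Protocol*

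**What the plan says.** Four places in the protocol bear on anticoagulants.

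- **At entry.** Criterion 17 in Section 3.4.2 excludes a subject who meets this description: "Requires or receiving anticoagulation with warfarin or equivalent vitamin K antagonists (eg, phenprocoumon) within 28 days of first dose of study drug". The synopsis prints the same criterion in the same words.
- **On study, prohibition.** Section 3.6.4 is a single sentence that lists forbidden therapies. Its closing part reads "kinase inhibitors, bone marrow transplantation, experimental therapy, warfarin, and radiotherapy are prohibited". Warfarin is the only anticoagulant in the list.
- **On study, caution.** Section 3.7.3 states "Serious hemorrhagic events, including fatal events, have occurred in clinical trials with acalabrutinib". For antithrombotic drugs in general it then advises: "Use caution with antithrombotic agents and consider additional monitoring for signs of bleeding when concomitant use is medically necessary".
- **On study, general safeguard.** Section 3.8 says that a participant "whose medical condition substantially changes after entering the study should be carefully evaluated by the investigator in consultation with the Acerta Pharma medical monitor", and adds: "Such subjects should be withdrawn from study treatment if continuing would place them at risk".

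The concomitant-medication entry in the synopsis deals with acid-reducing agents, BCRP substrates and CYP3A inhibitors and inducers. It does not mention anticoagulants.

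**The concern.** The protocol itself defines the group: for entry, it calls certain drugs equivalent to warfarin and handles them together with it. On study the ban is kept for warfarin and not stated for the rest of the group, and no reason is given for separating them.

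What is at stake is which drugs a site may start. Under the text as it stands, warfarin on study is a breach of Section 3.6.4 and phenprocoumon is not. With about 9 sites in up to 4 countries (Section 3.1), some may read the word warfarin as covering its equivalents and others may not. Safety is the primary objective, and bleeding is a recognised risk of the study drug, so one clear rule is worth having.

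**Working it through.** No arithmetic applies, because the protocol attaches no figure to this rule. The check is a comparison of texts.

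1. **Scope of the entry rule.** Criterion 17 covers warfarin and equivalent vitamin K antagonists, with phenprocoumon as an example. It governs eligibility. Once a subject is enrolled, it no longer decides which drugs may be added.
2. **Scope of the on-study ban.** Section 3.6.4 covers warfarin and, outside anticoagulation, several other therapies. It has no wording that reaches other vitamin K antagonists.
3. **Does another section extend the ban?** Section 3.7.3 covers antithrombotic agents as a whole, but it asks for caution and possible extra monitoring where use is medically necessary. That permits use. Section 3.8 calls for evaluation with the medical monitor when a subject's condition changes substantially, and for withdrawal if continuing is unsafe. That is a judgement on the individual subject, not a rule on the drug. The synopsis adds nothing. So the ban is not extended anywhere.
4. **Result for a drug started after enrollment.**

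| Drug started on study | Criterion 17 group? | Section 3.6.4 | What else applies |
|---|---|---|---|
| Warfarin | Yes | Prohibited | Sections 3.7.3 and 3.8 |
| Phenprocoumon or another equivalent vitamin K antagonist | Yes | Not prohibited | Sections 3.7.3 and 3.8 only |
| Other antithrombotic agent | No | Not prohibited | Sections 3.7.3 and 3.8 only |

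The second row is the inconsistency. A drug that criterion 17 places with warfarin is handled on study like the drugs outside the group.

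5. **Could the case arise?** Section 3.7.7 reports atrial fibrillation and flutter with acalabrutinib and leaves management to institutional guidelines, without a pointer to any limit on anticoagulants. That such guidelines may call for anticoagulation is a clinical inference and is not stated in the protocol. The case is therefore possible, but its frequency cannot be derived.

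**The case against.** The strongest reply is that little exposure is left uncovered. Criterion 17 removes subjects who already need or take these drugs. What remains is a new need after entry, met with a non-warfarin vitamin K antagonist. Section 3.7.3 then supplies a bleeding warning, a caution and a prompt to monitor. Concomitant medications are checked throughout treatment (Appendix 4) and recorded until 30 days after the last dose (Section 4.1.4). Section 3.8 brings in the medical monitor if the subject's condition changes substantially. A site that has just screened under criterion 17 may also read warfarin as shorthand for the group.

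Most of this stands, and it is why the point is minor. It does not remove the mismatch. If caution were judged enough for vitamin K antagonists, the outright ban on warfarin would be hard to explain. Sites may infer the wider meaning, but Section 3.6.4 does not state it.

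Three stronger readings are tempting, and the protocol does not support them.

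- A reader might take "corticosteroids (> 10 mg of prednisone or equivalent" in the same sentence as proof that the authors extended one named drug to its equivalents and forgot to do so for warfarin. There the banned item is the class of corticosteroids, and prednisone or its equivalent is the unit for the 10 mg threshold. It is not a parallel drug ban and shows nothing about warfarin.
- A reader might count the synopsis and Section 3.4.2 as two statements against one. They are one criterion printed twice, so the comparison is one entry criterion with one on-study list.
- A reader might infer that a rule stricter at entry than on study is a fault in itself. It is not. Criterion 18 excludes subjects who require long-acting proton pump inhibitors, whereas Section 3.6.3 only advises against these drugs on study. The fault here is narrower: the ban is kept for one member of a group and not stated for the others.

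**Conclusion.** The inconsistency is real and minor. Followed as written, Section 3.6.4 lets a site start phenprocoumon on study but not warfarin, although criterion 17 treats them as equivalent. The hazard is not uncontrolled: the gap is between caution and prohibition for the non-warfarin members of one drug group.

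Its size in subjects cannot be derived from the protocol, and no estimate is offered. The trial plans 20 subjects, and the gap affects only those who newly need anticoagulation and are given such a drug. No sample size, endpoint, analysis set or summary changes.

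The conclusion assumes that criterion 17 applies at entry only and that on-study use is governed by Section 3.6.4 as worded. Section 3.6.4 gives no reason for the warfarin ban. Bleeding is the likely one, by inference from Section 3.7.3. The safety relevance rests on that inference; the mismatch in wording does not.

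**What to change.** In Section 3.6.4, replace the single word warfarin with the group as criterion 17 names it: warfarin or equivalent vitamin K antagonists, with phenprocoumon as the example. Section 3.7.3 needs no change, and other antithrombotic agents stay under its caution.

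The cost is one phrase at the next amendment, with no extra visits, data or subjects. The downside is slightly less choice of anticoagulant for a subject who develops a need for one on study.
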